7.2.4 Secondary Biomarker Objectives

7.2.4.1 Second Biomarker Objective

To evaluate the effect of pembrolizumab on AML blast-reactive T-cells by quantification of activated T and NK cells, which are predicted to increase, and Tregs, which are predicted to decrease. The changes in these markers from baseline after treatment will be assessed by paired comparison t-test or Wilcoxon rank sum test, as appropriate. All point estimates will be accompanied by appropriate 95% confidence intervals. In all secondary biomarker analyses, observations with missing data will be excluded.

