2.3 Exploratory Objective

- (1) Objective: To evaluate the effect of pembrolizumab on AML blast-reactive T-cells by quantification of activated T and NK cells, which are predicted to increase, and regulatory T cells (Treg), which are predicted to decrease
- (2) Objective: To evaluate the effect of pembrolizumab on AML blast-reactive T-cells through functional analysis, through assessment of cytokine and Granzyme B/perforin expression in response to blast antigens.
- (3) Objective: To evaluate the effect of pembrolizumab on the immunosuppressive activity of exosomes, measured by their effects on NK-cell activity and T-cell expansion.

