Data interpretation and considerations: The proportions and absolute numbers of total and activated (CD69+/ CD25+) CD8+ T-cells, total and activated CD4+ Tcells, and CD3-CD56+ NK cells in AML patients at diagnosis and prior to pembrolizumab will be compared to values obtained with PBMC of healthy donors. These values in AML patients are expected to be lower than the established normal, suggesting the presence of T-cell suppression and/or apoptosis. Following pembrolizumab therapy, these values are expected to increase. Tregs (CD4+CD39+FOXP3+ and CD4+FOXP3+CD25+PD-1+) are expected to be elevated in frequency and absolute numbers in AML patients prior to pembrolizumab therapy. We expect Treg percentages/absolute numbers to decrease after pembrolizumab therapy based on the hypothesis that this Ab targets PD-1+ Treg and eliminates them. Expression of PD-1 is expected to decrease after therapy. This would suggest that pembrolizumab restores anti-leukemia immune responses not only by removing the checkpoint blockade and allowing for immune cell activation but also by removing Treg-mediated suppression.

3.2.3.2.2 T-cell expression of IFN- γ and Granzyme B/Perforin in T-cells stimulated *in vivo* with autologous AML blast-derived antigens

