Assay Performance: This is a two-step assay selected for monitoring of immune cell (T and NK cell) responses to a mix of blast-derived antigens. [54] This is an autologous system, with PBMC serving as APC. The assay can be readily adapted to serial monitoring. PBMC and autologous lysates will be cryopreserved and thawed for culture. Serially-collected specimens of each patient (as described in Section 4.2.3.2.1) will be batched and tested in one assay to avoid inter-assay variability. Culture controls set in parallel with patients' samples will be PBMCs of a normal donor (cryopreserved in bulk to supply the same control for all patients' cultures) stimulated with anti-CD3/CD28 Abs. Also, PBMCs of each evaluated AML patient will be stimulated with anti-CD3/CD28 Abs to serve as control for the ability to respond to TCR-mediated signals. 18h activation was previously shown to be a sufficient time period for induction of intra-cytoplasmic cytokines or GrB/perforin expression. [54] Multicolor flow cytometry assessments after cell permeabilization and staining with labeled antibodies to T and NK cell surface markers and the relevant cytokines are routinely performed on an instrument which is calibrated daily. The SOP for the assay is on file.

Data interpretation and considerations: This assay should be able to inform us about the ability of AML patients' immune cells to respond by cytokine or GrB/perforin expression to external stimulatory signals. [55] We expect from 10 to 15% of CD8+T cells of a normal donor to respond to activation with anti-CD3/CD28 Abs by up-regulating expression of these mediators. We expect to see a much lower frequency of responsive T-cells in AML patients. Only a small percentage of immune cells in AML patients (2-4%) are expected to respond to AML blast-derived lysates. Cells of normal donors (used as controls) are likely to respond but this will reflect alloantigen- rather than AML antigen-driven response. In patients receiving pembrolizumab, we expect to see recovery of T- cell responses to anti-CD3/CD28 Abs and of T and NK cell responses to antigens in AML blast-derived lysates by up-regulated expression of either IFN-g or GrB/perforin or both.

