| Treatment Cycle/Title: | Main Study Screening | 1 | 2 | 3 | 4 | To be repeated beyond 8 cycles | | | | Discon | Safety Follow-up | Follow Up Visits ^b | Survival Follow-Up |
| | | | | | | 5 | 6 | 7 | 8 | | | | |
| Scheduling Window (Days): | -28 to -1 | | ± 3 | ± 3 | ± 3 | ± 3 | ± 3 | ± 3 | ± 3 | At time of Discon | 30 days post discon | Every 12 weeks post discon | Every 12 weeks |
| T3, FT4 and TSH | X ^d | | X | | X | | X | | X | X | X | | |
| Chest radiograph | X | | | | | | | | | | | | |
| Bone marrow biopsy | X ^e | | | | | | | | X ^f | X ^f | | | |
| Archival or Newly Obtained Tissue Collection | X ^g | | | | | | | | | | | | |
| Correlative Studies Blood Collection ^h | | X | X | | X | | | | X ^h | X | | | |

a: Treatment cycles occur every 3 weeks, but may be given +/- 3 days of the scheduled dose. See Section 6.1.5.2

b: Follow-up CBC with differential should occur every 12 weeks +/- 7 days after discontinuation of therapy until disease progression, initiation of new anti-neoplastic therapy, death, end of study, re-treatment with pembrolizumab., or a total of 5 years from the subject's enrollment.

c: Pregnancy tests must occur within 72 hours of the first dose of pembrolizumab

d: All screening laboratory assessment must occur within 10 days prior to the first treatment

e: The screening bone marrow biopsy must be performed and read by a UPMC hematopathologist within 4 weeks prior to the 1st treatment cycle, and include flow cytometry and cytogenetic assessment. If possible, the screening bone marrow biopsy should be sent to the Fred Hutchinson Cancer Center for multiparameter flow cytometric minimal residual disease testing.

f: Bone marrow biopsy for efficacy assessment should occur at one year (between treatment cycle 16-18), and at treatment discontinuation (due to completion of 2 years, toxicity, or relapse) and include flow cytometry and cytogenetic assessment.

g: Subject should be assessed for achieved marrow or peripheral leukemic blasts from diagnosis of AML at screening visit

h: Correlative blood draws may be collected up to two (2) days prior to dosing. Blood collection for correlative studies should occur prior to cycle 1, 2, 4, 8, 17 (+/-1 treatment cycle), and at disease progression or the end of 2 years of treatment, whichever comes first.

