7.2.4.2 Secondary Biomarker Objective

To evaluate the effect of pembrolizumab on AML blast-reactive T-cells through functional analysis, through assessment of cytokine and Granzyme B/perforin expression in response to blast antigens. The analysis plan is similar to 7.2.4.1.

[figure not shown]
7.2.4.3 Secondary Biomarker Objective: *To evaluate the effect of pembrolizumab on the immunosuppressive activity of exosomes, measured by their effects on NK-cell activity and T-cell expansion.* The analysis plan is similar to 7.2.4.1.

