7.4 Justification of Design

The plot presents the power of the hypothesis test of the primary efficacy endpoint against the median TTR after *pembrolizumab* treatment. It is seen that 80% power is achieved (at $\alpha=0.1$ in a one-sided test) if the true median TTR is 19.5 months or greater. The stopping rule is based on a beta-binomial probability model that stops the trial if $PP(P(\text{Toxicity}) > 0.2) > 0.8$, where PP is the posterior probability function for $P(\text{Toxicity})$. The posterior model includes a binomial data model and a Beta(2,8) prior for the $P(\text{Toxicity})$. The plot displays the operating characteristics of the rule as a function of the true (unobserved) probability of toxicity. It is seen that, for instance, if the true probability of toxicity is 0.4, the probability the trial will stop early is 0.5, and the expected number of patients accrued is 28.

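### Section 7.2.4.1 names the Wilcoxon rank sum test, a test for independent samples, for within-patient change from baseline; the paired test is the Wilcoxon signed-rank test.

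*Combined protocol and SAP*

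**What the plan says.** Section 7.2.4.1 covers activated T cells, NK cells and Tregs. It states that their changes from baseline "will be assessed by paired comparison t-test or Wilcoxon rank sum test, as appropriate". It also promises 95% confidence intervals for all point estimates and excludes observations with missing data. For the functional markers, Section 7.2.4.2 says "The analysis plan is similar to 7.2.4.1"; Section 7.2.4.3 says the same for exosomes.

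The data are serial samples from the same treated patients. Section 4.3 describes a single arm in which every subject receives pembrolizumab. Footnote h of the Study Flow Chart (Section 5.1) sets blood draws before cycles 1, 2, 4, 8 and 17, and at progression or the end of two years.

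Section 3.2.3.2.1 plans one comparison of independent groups: T- and NK-cell values in patients at diagnosis and before pembrolizumab "will be compared to values obtained with PBMC of healthy donors". No test is named for it.

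The status of these objectives differs by section. They appear under "2.3 Exploratory Objective", while Section 7.2.4 heads them as secondary.

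**The concern.** The two options in one sentence treat the same data differently. The paired t-test works on each patient's difference. The rank sum test discards the link between a patient's two values and treats baseline and post-treatment values as coming from different people. Its null variance is then too large whenever a patient's values are positively correlated. The test rejects too rarely, and the power that pairing should bring is lost.

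A positive correlation is plausible for the functional assay. Section 3.2.3.2.2 says each patient's serial specimens "will be batched and tested in one assay to avoid inter-assay variability", so they share assay variation that a paired test removes and the rank sum test does not. That batching statement is made for the functional assay only, not for the cell counts in 7.2.4.1.

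What is at stake is a missed biomarker change in up to three objectives. An inflated false-positive rate is not at issue.

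**Working it through.** **What can be reproduced.** The plan gives no power, effect size, SD or correlation for the biomarkers, so it has no figure of its own to check. Every correlation and shift below is an assumption.

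**Direction and rough size by formula.** Let both time points have SD σ, with within-patient correlation ρ and n pairs. The variance of the mean change is 2σ²(1−ρ)/n. An unpaired test assumes 2σ²/n. Its test statistic therefore has SD √(1−ρ) under the null, and its true two-sided size at nominal 0.05 is about 2Φ(−1.96/√(1−ρ)):

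- ρ = 0: 1.96/1.000 = 1.96, size 5.0%
- ρ = 0.3: 1.96/0.837 = 2.34, size 1.9%
- ρ = 0.5: 1.96/0.707 = 2.77, size 0.56%
- ρ = 0.7: 1.96/0.548 = 3.58, size 0.03%

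**Simulation of the two Wilcoxon tests.** There were 10,000 paired samples per setting, at two-sided 0.05 (matching the promised 95% intervals). Data were bivariate normal or its exponential (lognormal, with shift and correlation set on the log scale). The full sample of n = 40 comes from Section 7.1, and the shift is 0.5 SD.

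| ρ | Rank sum size, normal | Power, normal: rank sum / signed-rank | Loss (points) | Power, lognormal: rank sum / signed-rank | Loss (points) |
|---|---|---|---|---|---|
| 0 | 4.77% | 57.8 / 57.1% | −0.7 | 57.4 / 51.5% | −5.9 |
| 0.3 | 2.06% | 57.6 / 70.8% | 13.2 | 58.5 / 65.5% | 7.0 |
| 0.5 | 0.75% | 61.1 / 85.9% | 24.8 | 59.6 / 78.1% | 18.5 |
| 0.7 | 0.07% | 63.2 / 97.3% | 34.1 | 64.0 / 94.1% | 30.1 |

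A negative loss means rank sum did better. The simulated sizes agree with the formula to within about 0.2 percentage points. Signed-rank size stayed between 4.2% and 5.0% in every setting.

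**Dependence on effect size (n = 40).** At 0.25 SD the loss is 7–10, 17–21 and 35–42 points at ρ = 0.3, 0.5 and 0.7. At 0.8 SD it is at most about 2 points. A separate normal-data run at 0.4 SD (5,000 samples per setting) gave rank sum / signed-rank power of 0.42/0.40, 0.39/0.53, 0.36/0.66 and 0.36/0.88 at ρ = 0, 0.3, 0.5 and 0.7, the same pattern.

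**Fewer pairs at later visits.** Cycle 17 starts after 16 × 3 = 48 weeks, or 11.04 months. Section 7.2.1 takes an exponential model with 26% relapse-free at two years: median = 24 × ln 2 / (−ln 0.26) = 12.35 months, which the plan gives as 12.3. Section 7.4 puts 80% power at a median of 19.5 months.

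- Median 12.3 months: 0.5^(11.04/12.3) = 0.537, and 40 × 0.537 = 21.5 patients (21 simulated)
- Median 19.5 months: 0.5^(11.04/19.5) = 0.675, and 40 × 0.675 = 27.0 patients

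Loss at 0.5 SD, in points (normal / lognormal):

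| n | ρ = 0.3 | ρ = 0.5 | ρ = 0.7 |
|---|---|---|---|
| 27 | 12.7 / 7.2 | 28.4 / 21.7 | 51.0 / 44.3 |
| 21 | 11.7 / 5.9 | 25.9 / 19.7 | 51.5 / 43.1 |

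These two sample sizes are illustrations. They count relapse as the only reason for leaving, and Section 3.2.1 reports the two-year figure as disease-free survival. Earlier draws would have more pairs.

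**The case against.** The best defence is that this is a slip in a name with no effect on results. The sentence is about changes and opens with a paired test. In a single-arm trial, the changes at one visit form one sample, and a rank sum test cannot be run on one sample. To follow the wording, an analyst would have to set the changes aside and compare raw baseline with raw post-treatment values as two groups. The closing qualifier might also be read as leaving room for the right test. If so, the power loss is zero.

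Much of this stands. The documents cannot show whether the name is a slip, and every loss above applies only if the non-parametric branch is chosen and run as named. But the qualifier chooses between two named tests, and only one of them is paired. Because the signed-rank test appears nowhere, a literal reader has no paired non-parametric option.

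A second defence is that rank sum was meant for the healthy-donor comparison, where it would be valid. That reading fails: the sentence is limited to change from baseline after treatment and does not mention donors.

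It is also fair to say that the magnitude is wholly conditional. It runs from rank sum being about 6 points better (ρ = 0, lognormal) to about 52 points worse (ρ = 0.7, n = 21).

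**Conclusion.** The concern holds, as a minor point. The named non-parametric test does not match paired data, and the mismatch carries to all three biomarker objectives. Used literally under positive within-patient correlation, it errs toward missing changes. With 40 pairs and a 0.5 SD shift, the loss is 7 to 13 points of power at correlation 0.3, rising to 30 to 34 at 0.7. It is absent at correlation 0 and close to nil for shifts of 0.8 SD. The correlation, shift and distribution are assumptions; only the sample size of 40 comes from the plan. The primary time-to-relapse test, the toxicity stopping rule, overall survival and the sample size are unaffected.

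**What to change.** In Section 7.2.4.1, replace the rank sum test with the Wilcoxon signed-rank test, and let the change carry to 7.2.4.2 and 7.2.4.3. If a test is to be named for the patient versus healthy-donor comparison in Section 3.2.3.2.1, the rank sum test belongs there.

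Two additions are useful but optional:

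- Name the Hodges-Lehmann estimate with its 95% interval as the companion to the signed-rank test, since the section already promises intervals.
- State before the data are seen when each test applies and whether counts are log-transformed.

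The cost is one test name and a line or two of text, with no new data or visits. There is one trade-off. The Hodges-Lehmann estimate equals the median change only if the paired differences are roughly symmetric, so right-skewed counts may need the log scale. If the within-patient correlation were zero and the data skewed, signed-rank on the raw scale would give up about 5 to 6 points of power against rank sum.

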7.2.4.2 Secondary Biomarker Objective

To evaluate the effect of pembrolizumab on AML blast-reactive T-cells through functional analysis, through assessment of cytokine and Granzyme B/perforin expression in response to blast antigens. The analysis plan is similar to 7.2.4.1.

[figure not shown]
7.2.4.3 Secondary Biomarker Objective: *To evaluate the effect of pembrolizumab on the immunosuppressive activity of exosomes, measured by their effects on NK-cell activity and T-cell expansion.* The analysis plan is similar to 7.2.4.1.

7.3 Stopping Rule for Excess Toxicity

The table displays the stopping rule for excessive toxicity. Excessive toxicity is defined as any drug-related toxicity that results in withholding or discontinuation of pembrolizumab. Additionally, any unexpected grade 3-4 AEs will be defined as excessive toxicity.”

| # Patients | #Toxicities |
|------------|-------------|
| 5 | 3 |
| 10 | 4 |
| 15 | 5 |
| 20 | 7 |
| 25 | 8 |
| 30 | 9 |
| 35 | 10 |

[figure not shown]
The trial is suspended if the number of toxicities is greater than or equal to the number in the second column. For instance, if 5 out of the first 15 patients experience severe toxicity,

the trial is suspended if the number of toxicities is greater than or equal to the number in the second column. For instance, if 5 out of the first 15 patients experience severe toxicity, the trial is suspended.

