4.2.1.2 Dose Modification

Adverse events (both non-serious and serious) associated with Pembrolizumab exposure may represent an immunologic etiology. These adverse events may occur shortly after the first dose or several months after the last dose of treatment. Adverse experiences will be graded and recorded throughout the study and during the follow-up period according to NCI CTCAE Version 4.0. Pembrolizumab must be withheld for drug-related toxicities and severe or life-threatening drug-related AEs as per Table 3 below. See Section 4.6.1 and Events of Clinical Interest Guidance Document for supportive care guidelines, including use of corticosteroids.

**Table 3
Dose Modification Guidelines for Drug-Related Adverse Events**

| Toxicity | Hold Treatment For Grade | Timing for Restarting Treatment | Discontinue Subject |
|----------------------------------|--------------------------|---------------------------------|--|
| Diarrhea/Colitis | 2-3 | Toxicity resolves to Grade 0-1. | Toxicity does not resolve within 12 weeks of last dose or inability to reduce corticosteroid to 10 mg or less of prednisone or equivalent per day within 12 weeks. |
| | 4 | Permanently discontinue | Permanently discontinue |
| AST, ALT, or Increased Bilirubin | 2 | Toxicity resolves to Grade 0-1 | Toxicity does not resolve within 12 weeks of last dose. |

| Toxicity | Hold Treatment For Grade | Timing for Restarting Treatment | Discontinue Subject |
|---|--------------------------|---|--|
| | 3-4 | Permanently discontinue | Permanently discontinue |
| Type 1 diabetes mellitus (if new onset) or Hyperglycemia | T1DM or 3-4 | Hold Pembrolizumab for new onset Type 1 diabetes mellitus or Grade 3-4 hyperglycemia associated with evidence of beta cell failure. | Resume Pembrolizumab when patients are clinically and metabolically stable. |
| Hypophysitis | 2-3 | Toxicity resolves to Grade 0-1 | Toxicity does not resolve within 12 weeks of last dose or inability to reduce corticosteroid to 10 mg or less of prednisone or equivalent per day within 12 weeks. |
| | 4 | Permanently discontinue | Permanently discontinue |
| Hyperthyroidism | 3 | Toxicity resolves to Grade 0-1 | Toxicity does not resolve within 12 weeks of last dose or inability to reduce corticosteroid to 10 mg or less of prednisone or equivalent per day within 12 weeks. |
| | 4 | Permanently discontinue | Permanently discontinue |

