4.8 Subject Withdrawal/Discontinuation Criteria

Subjects may withdraw consent at any time for any reason or be dropped from the trial at the discretion of the investigator should any untoward effect occur. In addition, a subject may be withdrawn by the treating sub-investigator or the Principal Investigator if enrollment into the trial is inappropriate, the trial plan is violated, or for administrative and/or other safety reasons. Specific details regarding discontinuation or withdrawal are provided in Section 6.1.4 – Other Procedures.

A subject must be discontinued from the trial for any of the following reasons:

- The subject or legal representative (such as a parent or legal guardian) withdraws consent.
- Confirmed pathologic disease progression
- Unacceptable adverse experiences as described in Section 6.2.1.2
- Intercurrent illness that prevents further administration of treatment
- Investigator's decision to withdraw the subject
- The subject has a confirmed positive serum pregnancy test

- Noncompliance with trial treatment or procedure requirements
- The subject is lost to follow-up
- Completed 24 months of treatment with pembrolizumab and required follow-up
- Administrative reasons

The End of Treatment and Follow-up visit procedures are listed in Section 5 (Trial Flow Chart) and Section 6.1.5 (Visit Requirements). After the end of treatment, each subject will be followed for 30 days for adverse event monitoring (serious adverse events will be collected for 90 days after the end of treatment as described in Section 6.2.3.1). Subjects who discontinue for reasons other than progressive disease will have post-treatment follow-up for disease status until disease progression, initiating a non-study cancer treatment, withdrawing consent or becoming lost to follow-up. After documented disease progression each subject will be followed by telephone for overall survival until death, withdrawal of consent, or the end of the study, whichever occurs first.

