4.10 Clinical Criteria for Early Trial Termination

Early trial termination will be the result of the criteria specified below:

1. Quality or quantity of data recording is inaccurate or incomplete
2. Poor adherence to protocol and regulatory requirements
3. Incidence or severity of adverse drug reaction in this or other studies indicates a potential health hazard to subjects
4. Plans to modify or discontinue the development of the study drug

In the event of Merck decision to no longer supply study drug, ample notification will be provided so that appropriate adjustments to subject treatment can be made.

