6.2 Assessing and Recording Adverse Events

An adverse event is defined as any untoward medical occurrence in a patient or clinical investigation subject administered a pharmaceutical product and which does not necessarily have to have a causal relationship with this treatment. An adverse event can therefore be any unfavorable and unintended sign (including an abnormal laboratory finding, for example), symptom, or disease temporally associated with the use of a medicinal product or protocol-specified procedure, whether or not considered related to the medicinal product or protocol-specified procedure. Any worsening (i.e., any clinically significant adverse change in frequency and/or intensity) of a preexisting condition that is temporally associated with the use of the investigational product, is also an adverse event.

Changes resulting from normal growth and development that do not vary significantly in frequency or severity from expected levels are not to be considered adverse events. Examples of this may include, but are not limited to, teething, typical crying in infants and children and onset of menses or menopause occurring at a physiologically appropriate time.

Adverse events may occur during the course of the use of the investigational product in clinical trials or within the follow-up period specified by the protocol, or prescribed in clinical practice, from overdose (whether accidental or intentional), from abuse and from withdrawal.

Adverse events may also occur in screened subjects during any pre-allocation baseline period as a result of a protocol-specified intervention, including washout or discontinuation of usual therapy, diet, placebo treatment or a procedure.

All adverse events will be recorded from the time the consent form is signed through 30 days following cessation of treatment and at each examination on the Adverse Event case report forms/worksheets. The reporting timeframe for adverse events meeting any serious criteria is described in section 6.2.3.1.

Adverse events will not be collected for subjects during the pre-screening period (for determination of archival tissue status) as long as that subject has not undergone any protocol-specified procedure or intervention. If the subject requires a blood draw, fresh tumor biopsy etc., the subject is first required to provide consent to the main study and AEs will be captured according to guidelines for standard AE reporting.

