6.2.3 Immediate Reporting of Adverse Events to the Investigator and to Merck

6.2.3.1 Serious Adverse Events

A serious adverse event is any adverse event occurring at any dose or during any use of the investigational product that:

- Results in death;
- Is life threatening;
- Results in persistent or significant disability/incapacity;
- Results in or prolongs an existing inpatient hospitalization;
- Is a congenital anomaly/birth defect;
- Is a new cancer (that is not a condition of the study);
- Is associated with an overdose;
- Is another important medical event

Progression of the cancer under study is not considered an adverse event unless it results in hospitalization or death.

Any serious adverse event, or follow up to a serious adverse event, including death due to any cause other than progression of the cancer under study that occurs to any subject from the time the consent is signed through 90 days following cessation of treatment, or the initiation of new anti-cancer therapy, whichever is earlier, whether or not related to the investigational product, must be reported within 24 hours to the Investigator and within 2 working days to Merck Global Safety.

Non-serious Events of Clinical Interest will be forwarded to Merck Global Safety and will be handled in the same manner as SAEs.

Additionally, any serious adverse event, considered by an investigator who is a qualified physician to be related to the investigational product that is brought to the attention of the investigator at any time outside of the time period specified in the previous paragraph also must be reported immediately to the Investigator and to Merck.

SAE reports and any other relevant safety information are to be forwarded to the Merck Global Safety [contact]

All subjects with serious adverse events must be followed up for outcome.

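### The toxicity count in Section 7.3 omits some severe drug-related events that first appear after pembrolizumab was stopped for a non-toxicity reason: a narrow gap that one sentence would close

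*Combined protocol and SAP*

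**What the plan says.** Section 7.3 defines the event that the stopping boundary counts. Limb 1: "Excessive toxicity is defined as any drug-related toxicity that results in withholding or discontinuation of pembrolizumab". Limb 2: "Additionally, any unexpected grade 3-4 AEs will be defined as excessive toxicity". Accrual is suspended when the count reaches the tabulated number at 5, 10, ... 35 patients. Section 7.4 derives the boundary from a Beta(2,8) prior, a toxicity threshold of 0.2 and a posterior cut-off of 0.8.

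Section 4.2.1.2 says of pembrolizumab-associated events: "These adverse events may occur shortly after the first dose or several months after the last dose of treatment". For patients on drug it requires action: "Pembrolizumab must be withheld for drug-related toxicities and severe or life-threatening drug-related AEs as per Table 3 below".

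Section 4.8 lists reasons for stopping that are not toxicity, among them confirmed progression and "Intercurrent illness that prevents further administration of treatment".

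Late events are collected. Section 6.2: "All adverse events will be recorded from the time the consent form is signed through 30 days following cessation of treatment". Section 6.2.3.1 takes serious events "through 90 days following cessation of treatment, or the initiation of new anti-cancer therapy, whichever is earlier". Section 6.2.3.2 has a similar 90-day window for events of clinical interest.

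**The concern.** Limb 1 depends on a dosing action. A patient who has already stopped drug has no dose left to withhold, so a drug-related event that begins after a relapse-driven stop cannot meet limb 1, however severe it is. Limb 2 requires the event to be unexpected and Grade 3-4. An expected late Grade 3-4 event, or a late event first recorded as Grade 5, therefore falls outside both limbs, and no other text adds it to the count.

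The result is uneven. A Grade 2 colitis that leads to a hold counts. An expected Grade 4 colitis that appears two weeks after a stop for relapse does not.

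What is at stake is the formal trigger. A numerical boundary exists so that suspension does not rest on judgement alone, and here its count can leave out a severe event that is foreseen and already in the database.

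**Working it through.** **1. The plan's own figures.** Under Section 7.4 the boundary at n patients is the smallest x with P(p > 0.2 | Beta(2+x, 8+n−x)) > 0.8. All seven tabulated counts reproduce:

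| n | boundary x | posterior at x | posterior at x−1 |
|---|---|---|---|
| 5 | 3 | 0.870 | 0.698 |
| 10 | 4 | 0.837 | 0.673 |
| 15 | 5 | 0.811 | 0.656 |
| 20 | 7 | 0.892 | 0.790 |
| 25 | 8 | 0.875 | 0.773 |
| 30 | 9 | 0.859 | 0.759 |
| 35 | 10 | 0.846 | 0.746 |

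An exact binomial recursion over these looks (maximum 40 patients) gives stopping probabilities of 0.282, 0.741 and 0.964 at true rates of 0.20, 0.30 and 0.40. Section 7.4 states 0.5 and an expected accrual of 28 at a rate of 0.40, where the recursion gives 0.964 and 12.9. That mismatch is a separate matter and is not used here.

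**2. Which events the definition reaches.**

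| Drug-related event | Limb 1 | Limb 2 | Counted |
|---|---|---|---|
| On drug, Grade 3-4, Table 3 requires hold or stop | yes | if unexpected | yes |
| On drug, expected Grade 3-4 hypothyroidism, or cytopenia above the no-hold cut-offs in 4.2.1.2 | no, if dosing continues | no | no |
| First seen after a non-toxicity stop, unexpected Grade 3-4 | no | yes | yes |
| First seen after a non-toxicity stop, expected Grade 3-4 | no | no | **no** |
| First seen after a non-toxicity stop, first recorded as Grade 5 | no | no | **no** |

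The no-hold cut-offs are platelets of at least 30,000/mcL and ANC of at least 500/mcL. A patient who stopped because of drug toxicity has already been counted. The point concerns the last two rows.

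**3. Size, as an illustration.** The documents give no late-event rate. Assumptions:
- 40 patients accrue evenly over 18 or 24 months (Trial Summary).
- Exponential relapse, with a median of 12.3 or 19.5 months (7.2.1, 7.4), is the only reason for stopping.
- The toxicity hazard is constant on drug and for w days after relapse.
- A fraction f = 0.5 of toxicities is Grade 3 or higher, and all of these are classed as expected.

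With λ = ln 2 / median and t the time since enrolment, expected time on drug is A(t) = (1 − e^(−λt))/λ. Expected time at risk after stopping is B(t) = ∫₀ᵗ λe^(−λu) min(w, t−u) du. The uncounted share at look n is s = f ΣB / (ΣA + ΣB), summed over the first n patients. The expected count at look n becomes n·p·(1 − s), and the recursion is rerun with those rates.

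Three choices of w:
- 30 days: every patient has the full window after relapse.
- 19.5 days: 6.1.5.3.1 times the safety visit from the last dose. With 21-day cycles and relapse falling evenly between doses, 30 − 10.5 = 19.5.
- 9 days: relapse is found at the next cycle visit, 30 − 21 = 9.

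| w (days) | P(stop) at true rate 0.30 | loss from 0.741 |
|---|---|---|
| 30 | 0.712-0.723 | 0.018-0.029 |
| 19.5 | 0.722-0.729 | 0.012-0.019 |
| 9 | 0.732-0.735 | 0.006-0.009 |

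At w = 30 the uncounted share at 35 patients is 1.6-2.5%. At a true rate of 0.30 that is 35 × 0.30 × 0.016 to 0.025, or about 0.2 to 0.3 of a patient. With f = 0.25, P(stop) at 0.30 is 0.727-0.732.

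If the uncounted share were simply set at 2%, 5% or 10%, P(stop) at 0.30 would be 0.718, 0.681 or 0.614. Nothing in the documents points to the larger shares.

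**The case against.** The strongest reply is that this is a matter of preference. Counting toxicities that interrupt dosing is a coherent tolerability rule. Late events are still tabulated under 7.2.2 and reported under 6.2.3. Section 4.10 allows termination when "Incidence or severity of adverse drug reaction in this or other studies indicates a potential health hazard to subjects", and Section 9.5 lets the DSMB and DSMC suspend accrual. All of that stands, and no safety information is lost. But those powers are discretionary, while 7.3 is a preset trigger.

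The illustration may also run high. New anti-cancer therapy after relapse closes the serious-event window early. The causality guidance in Table 10 steers attribution away from the drug when another cause is obvious. Some late events will be unexpected and so counted by limb 2. In the other direction, 90-day follow-up of SAEs and ECIs would raise the loss.

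That one patient can decide a look (0.811 at 5 of 15 against 0.656 at 4 of 15) is true of any threshold rule. It shows how a single omission could matter, not how often it would.

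A reader might infer three stronger things that the documents do not support:
- *The rule misses severe toxicity in general.* On drug, Table 3 captures nearly all Grade 3-4 drug-related events through limb 1.
- *Every drug-related death after stopping is missed.* Section 6.2.4 records each grade change, so an unexpected event that passes through Grade 3-4 before death counts under limb 2.
- *The rule under-detects toxicity overall.* Grade 2 holds count too, so no net direction can be claimed.

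**Conclusion.** The gap in the wording of 7.3 is real and narrow. It concerns a drug-related event that first appears after a non-toxicity stop and is either an expected Grade 3-4 event or first recorded as Grade 5. What 7.3 treats as expected is not defined there, so the edge of the gap is not sharp.

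The likely effect on the rule is small: a loss in stopping probability of about 0.01 to 0.02 at a true rate of 0.30, and up to 0.03 with a full 30 days at risk after relapse. These figures rest on the assumptions in the working, chiefly a constant hazard, relapse as the only reason for stopping, and half of toxicities being Grade 3 or higher. This is a low-priority improvement, worth making because it is cheap.

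**What to change.** Add to the definition in Section 7.3:

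> or any drug-related Grade 5 event, or any drug-related Grade 3-4 event with onset after the last dose and within the existing reporting windows (30 days for AEs; 90 days for SAEs and ECIs; or the protocol's new-therapy cut-off if earlier) that would have required withholding or discontinuation under Section 4.2.1.2 had the patient still been on drug; each patient counts once.

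The last condition keeps on-drug and off-drug events on the same footing. Without it, expected Grade 3-4 hypothyroidism, or a cytopenia above the no-hold cut-offs, would count after the last dose but not during dosing.

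Keep the boundary table. It depends only on the prior, the 0.2 threshold and the 0.8 cut-off.

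The change needs no new visits or data. It asks the investigator for one extra judgement per late event, made against Table 3 and the cytopenia rules. Suspension becomes very slightly more likely: at a true rate of 0.20, at most from about 0.26-0.27 to 0.28.
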